6.2 Setting

Because NMOSD is a rare disease and inebilizumab is a novel therapy, it is crucial to identify data sources with sufficiently large and representative patient populations to evaluate patterns of use and the safety profile of the drug in real-world practice (section 6.5). Data sources in 5 European countries: France, Germany, Italy, the Netherlands and Spain were selected for use in this study. The study population will be identified in national healthcare administrative databases, claim databases, and disease-specific registries. Please refer to section 6.4 for further details on the selected data sources.

Throughout the study period data will be extracted annually and the number of patients exposed to inebilizumab will be monitored to update and inform the study size. While patients will be followed up prospectively during the study period, data will be acquired

retrospectively at each data extraction time point according to the protocol and the statistical analysis plan (SAP).

Due to the nature of the study (a drug for a rare disease used in real-world clinical practice), limited inclusion and exclusion criteria will be applied; nevertheless, to minimize bias associated with existing users (including prevalence bias, survivor bias and follow-up bias), only first-time users during the study period will be analyzed.

6.2.1 Inclusion Criteria

An eligible population will consist of all inebilizumab users identified during study period in the selected databases. Within this population, patients who meet all the following criteria will be included for this study:

- First time administration/prescription/dispensation of inebilizumab, i.e., no inebilizumab treatment in the 6 months prior to index date
- Diagnosis of NMOSD before or at the index day
- At least 18 years old at index date

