4 RATIONALE AND BACKGROUND

4.1 Background

Neuromyelitis optica spectrum disorder (NMOSD; also known as Devic's syndrome and previously known as neuromyelitis optica [NMO]) is a rare, chronic, autoimmune, inflammatory disorder of the central nervous system, characterized by attacks of optic neuritis and longitudinally extensive transverse myelitis and, less frequently, affecting the brain and brainstem (1). Commonly reported symptoms include ocular pain, unilateral or bilateral loss of visual acuity that can lead to blindness, loss of sensation, weakness (including paraplegia), bladder and bowel dysfunction, paroxysmal tonic spasms of the trunk and limbs, and Lhermitte's phenomenon (1). Up to 90% of patients with NMOSD have recurring episodes of optic neuritis and/or myelitis rather than following a monophasic course (2). Attacks can be severe and result in blindness, paralysis, and even death due to neurogenic respiratory failure (3). An important paraclinical feature of NMOSD seen in 80% patients and used to help differentiate the condition from multiple sclerosis (MS) is the presence of serum autoantibodies against aquaporin-4 (AQP4) (i.e., AQP4-immunoglobulin [Ig]G or NMO-IgG) (4).

Worldwide, incidence rates of adult NMOSD are reportedly between 0.04-0.73/100,000 person-years (5), while the prevalence of NMOSD in adults is approximately 0.5-4/100,000 and may be up to 10/100,000 in certain racial groups (6). NMOSD can occur at any age, and disproportionately affects females (70%-90%), with a mean age of onset of approximately 40 years (6).

Treatment of NMOSD comprises 2 main goals: recovery from acute attacks and prevention of future attacks (relapse) as well as prevention of sequelae.

Recently, inebilizumab, an anti-CD19 B-cell depleting antibody, was approved for the treatment of NMOSD in AQP4-IgG seropositive patients in the US, Japan, and South Korea, and in November 2021 the Committee for Medicinal Products for Human Use of the European Medicines Agency (EMA) also recommended approval for the same patient population. The current recommended initial dose is 300 mg intravenous (IV) infusion followed 2 weeks later by a second 300 mg IV infusion. The recommended maintenance dose is a single 300 mg IV infusion every 6 months thereafter, starting 6 months from the first infusion (7).

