6 RESEARCH METHODS

6.1 Study Design

This will be a non-interventional multi-center cohort study of patients initiating inebilizumab conducted with secondary data sources in France, Germany, Italy, the Netherlands, and Spain. The study will be based on a cohort-event monitoring design to capture both drug utilization and selected safety outcomes in patients initiating inebilizumab. The proposed study design allows for an efficient initial descriptive evaluation of AESI.

The **study period** in individual countries will start on different dates, depending on the launching time of the drug (the earliest in the second quarter of 2022) (Table 1). The end of the study period will be also country-specific (the latest in December 2027) and will depend on the dates of data availability in individual data sources (different lag times and data release dates).

Table 1 Study periods, by country

	France	Germany	Italy	Netherlands	Spain
	SNDS/ NOMADMUS	GKV	RISM	PHARMO	SIDIAP
Launch date (quarter, year)	Q2, 2022	Q3, 2022	Q2 2023	Q3, 2023	Q2, 2023
Start of study period	May 2022	Aug 2022	May 2023	Aug 2023	May 2023
End of study period	Dec 2026	Dec 2026	Dec 2027	Dec 2026	Sep 2027
Study period duration (months)	57	54	56	41	53

Q2, 2nd quartile; Q3, 3rd quartile

The study population will be constituted by a cohort of adult female and male patients diagnosed with NMOSD with entry trigger by inebilizumab initiation.

[figure not shown]
The **index date** (Day 0) will be defined as the date of first treatment (date of administration/prescription/dispensation, depending on data available in selected data sources) (Figure 1). Patients initiating the treatment will be identified throughout the study period. After the index date, enrolled patients will be followed for 12 months or censored at end of study period or loss of follow-up (death, disenrollment/de-registering) whichever occurs first.

A **baseline period**, including any time from when data are available up to the index date, will be used to establish comorbidities and NMOSD-related clinical characteristics, whereas a short period of 6 months prior to or at index date will be used to determine previous immunosuppressive therapies.

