6.3.1 New Inebilizumab Users

This is an observational study of real-world clinical practices and this protocol does not recommend the use of any specific treatments.

New inebilizumab users will be defined as patients with a first inebilizumab treatment (identified through first administration/prescription/dispensation, depending on how the information on the drug is collected in the data sources) during the study period with no previous inebilizumab treatment in 6 months prior to the index date.

Inebilizumab treatment (first and each subsequent administration/ prescription/ dispensation) will be identified by the ATC code (L04AA47 / L04AG10 from 2024). Information accompanying every drug administration/prescription/dispensation, including date and time, dose, indication, setting of healthcare and specialty of prescriber will be retrieved, if available.

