6.3.3 Treatment patterns

During follow-up, treatment patterns will be characterized in terms of dose, treatment duration, frequency of drug discontinuation, switching and use of add-on therapies. All patients included in the study will be deemed exposed (at least one inebilizumab treatment), but only those with complete 12-month follow-up will be considered in the evaluation of the treatment patterns as described below.

According to the product specifications, the 12-month follow-up will cover 3 potential inebilizumab administrations: initial intravenous (IV) infusion followed by a second

infusion 2 weeks later and a subsequent infusion 6 months after the first treatment (Figure 2A). The first and third infusion will be considered in defining inebilizumab treatment patterns.

Treatment duration will be the sum of days under inebilizumab exposure during the follow-up. Number of days under exposure will be calculated for the first and the third infusion as the difference between end date of inebilizumab exposure period and the administration/prescription/dispensation date (Figure 2B).

[figure not shown]
Inebilizumab complete **exposure period** will be assumed to last 180 days after drug administration/prescription/dispensation. The **end date of the exposure** period will be defined as the end of each inebilizumab exposure period within follow-up or the end date of follow-up if comes first (Figure 2B).

A patient will be considered to be in inebilizumab **continuous use** if no gap longer than 60 days occurs between the end date of the first inebilizumab exposure period and the beginning of the third (2B). **Temporary discontinuation** (intermittent users) will be defined in patients with gaps between inebilizumab exposure periods longer than 60 days but with a subsequent inebilizumab administration/prescription/dispensation during the follow-up. A patient will be defined as having **permanently discontinued** inebilizumab if no subsequent inebilizumab treatment is registered during the follow-up after the end date of the first inebilizumab exposure period.

Switchers will be a subgroup of patients who discontinue inebilizumab (temporarily or permanently) during the follow-up and have other NMOSD maintenance drug administered/ prescribed (Table 9) after the end date of inebilizumab exposure period (2C). The alternative NMOSD drugs will be described.

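### The 6-month look-back for first-time inebilizumab use is no longer than the maintenance interval and no prior observation is required, so some existing users can enter as new users

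*Protocol*

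**What the plan says.** Section 6.2 gives the purpose: to limit the biases that come with existing users, "only first-time users during the study period will be analyzed".

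Section 6.2.1 makes this operational as "First time administration/prescription/dispensation of inebilizumab, i.e., no inebilizumab treatment in the 6 months prior to index date". Section 6.3.1 defines new users as those whose first treatment falls in the study period, "with no previous inebilizumab treatment in 6 months prior to the index date". Section 6.2.2 applies no exclusion criteria, and no section requires a minimum time under observation before the index date.

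Two other sections bear on whether six months is long enough. Section 4.1 gives maintenance infusions "every 6 months thereafter, starting 6 months from the first infusion". Section 6.3.3 says the exposure period "will be assumed to last 180 days after drug administration/prescription/dispensation", and counts use as continuous "if no gap longer than 60 days occurs between the end date of the first inebilizumab exposure period and the beginning of the third".

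Section 6.1 sets the index date at the first treatment, and it and Table 1 tie each country's study period to launch. It also lets comorbidities and NMOSD characteristics be taken from all earlier data, so a longer history is already being used for other variables.

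**The concern.** A new-user rule has to look back further than the longest interval at which a patient can still be on treatment. This one looks back exactly one maintenance interval. A maintenance infusion given slightly late has no inebilizumab record in the preceding six months, although section 6.3.3 would call the same interval continuous use. Where a source holds no earlier data on a patient, the criterion is met automatically.

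An existing user admitted at a maintenance infusion would distort three outputs:

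- **Infusion tables (section 6.7.2.2).** There is no two-week infusion after index. The infusion at about month 6 is counted as the second and the one at about month 12 as the third, so initiation and maintenance are mixed.
- **Continuous use (section 6.3.3).** The rule compares the end of the first exposure period with the start of the third. For this patient the gap is about 365 − 180 = 185 days, above the 60 allowed, so a patient treated on schedule is not classed as continuous.
- **Adverse events of special interest (section 6.7.2.3).** Time from index, and infusion-reaction incidence, would include people who have already been through earlier infusions.

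**Working it through.** The protocol prints no figure for this point that could be reproduced. The 240 days is derived below, and no sample-size quantity enters.

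**Inputs**

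- Look-back: 6 months (6.2.1, 6.3.1)
- Maintenance interval: 6 months, counted from the first infusion, with a second infusion 2 weeks after the first (4.1, 6.3.3)
- Exposure per infusion: 180 days (6.3.3)
- Tolerated gap: 60 days (6.3.3)
- Study start months: May 2022 to August 2023 (Table 1)

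**Step 1. Look-back against the continuous-use limit**

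- Six calendar months last 181 to 184 days, depending on the date.
- Longest interval still continuous: 180 + 60 = 240 days.
- Uncovered: 240 − 184 = 56 days to 240 − 181 = 59 days.

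Section 6.3.3 writes its rule for the first and third infusions. Carrying it over to later maintenance intervals is my step, because the protocol offers no other yardstick.

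**Step 2. Which infusions pass the look-back**

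Example with a first infusion on 1 January 2023, on schedule:

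| Infusion | Date | Days since previous | Previous infusion lies |
|---|---|---|---|
| 2 | 15 Jan 2023 | 14 | inside the window |
| 3 | 1 Jul 2023 | 167 | inside the window |
| 4 | 1 Jan 2024 | 184 | on the boundary |
| 5 | 1 Jul 2024 | 182 | on the boundary |

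- Infusion 3 is caught, because infusion 2 lies inside the window. It passes only if it is more than about two weeks late.
- Infusion 4 passes if it is one day late (185 days). It stays within 240 days until it is 240 − 184 = 56 days late. Over that span the look-back test and the continuous-use rule give opposite answers.
- As an assumption outside the protocol: if maintenance intervals centre on 183 days with an SD of 7 to 30 days, about 44% to 49% exceed 184 days. This is a share of maintenance intervals, not of the cohort.

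**Step 3. Who can reach such a dose as index**

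Section 6.3.1 also requires the treatment to be the first in the study period. For a patient observed and eligible since launch, infusion 4 is not the first, so it cannot be the index. Three routes remain:

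1. *Doses before the start month.* Table 1 starts every country in the middle month of its launch quarter (for example launch Q2 2022, start May 2022), so about one month of post-launch dosing can precede it. If infusions 1 and 2 both fell in that month, infusion 3 becomes the first in the study period and passes if more than about two weeks late.
2. *Doses before eligibility.* Section 6.2.1 requires an NMOSD diagnosis by the index date and age 18. Section 6.3.2 cites 42.5% initial misdiagnosis as MS in one retrospective study. If an earlier dose preceded the recorded diagnosis or the 18th birthday, a later dose more than six months after the last one meets all three inclusion criteria as worded. The protocol does not say whether such a patient may be indexed at the later dose.
3. *Joining a source on treatment.* The German data come from about 8 to 10 insurers (6.4.2), SIDIAP observation can begin on assignment to a centre (6.4.3), and the Italian register collects from accrual (6.4.4). Earlier doses are then not in the data, so the length of the look-back is irrelevant; what is missing is a condition on prior observation.

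**Step 4. Effect of the change**

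A look-back over all recorded history reduces the uncovered 56 to 59 days to 0 and closes routes 1 and 2 wherever the doses are recorded. Route 3 needs an observability flag.

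**The case against.** The strongest reply is that the six-month window is not the only test. The index must be the first treatment in a study period that begins at about launch, and this protects every patient observed and eligible from then on. That stands. A reader might infer that any continuously treated patient whose last infusion was six to eight months ago qualifies as a new user. The documents do not support that, because for most such patients the earlier infusion would itself be the first in the study period.

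The residual routes are also narrow in places. Route 1 covers about one month after launch, and the protocol describes no pre-launch use. SNDS covers 99% of the French population, with entry by birth or immigration (6.4.1), and mean follow-up is 10 years in SIDIAP and twelve in PHARMO (6.4.3, 6.4.5). These facts limit route 3 but do not remove it for the German insurers or the Italian register, nor for people newly assigned to a SIDIAP centre.

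It can also be said that operational detail belongs in the SAP. But the definition of first-time use is fixed in the protocol itself, in two places, and an SAP that follows it would inherit the weakness.

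A reader might extend the point to section 6.1, where "a short period of 6 months prior to or at index date will be used to determine previous immunosuppressive therapies", and conclude that other agents infused about twice a year are missed. The protocol gives no dosing intervals for those agents (Annex 3, Tables 9 and 10 list codes only), so that conclusion is not available here.

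Finally, a hard 240-day observability requirement could remove genuine initiators in a rare disease, and sections 6.2 and 6.2.2 deliberately keep the criteria few. That stands, and it shapes the fix.

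**Conclusion.** The point holds in a limited form. The six-month rule does not by itself secure the restriction to first-time users that section 6.2 promises: it equals the maintenance interval, falls 56 to 59 days short of the protocol's own 240-day limit for continuous use, and carries no condition on prior observation. The leak is confined to doses before the study start month, doses before a recorded diagnosis or age 18, and entry into a source while on treatment.

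The number of patients affected cannot be derived from the documents, so no bias in the infusion tables or in adverse-event incidence is demonstrated, only made possible. The 44% to 49% in the working is conditional on an assumed spread and must not be read as a share of the cohort. The conclusion rests on the literal wording of 6.2.1 and 6.3.1 and on applying the 240-day limit to later maintenance intervals. It is worth correcting before extraction because the correction is nearly free, not because a large effect has been shown.

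**What to change.** 1. In sections 6.2.1 and 6.3.1, define new use as no inebilizumab record at any time in the available data before the index date, including before the start of the study period. The index is then the first recorded dose, which also settles whether a patient ineligible at that dose can be indexed later.
2. Flag patients with less than 240 days of observability before index. Keep them in the main analysis and repeat the key treatment-pattern and adverse-event results without them as a sensitivity analysis.
3. Report the number flagged, and the number removed under item 1, by data source. The STROBE diagram in section 6.7.2 is a natural place. This supplies the size that the protocol cannot give now.

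Cost: short edits to two sections and a small amount of extra analysis. Section 6.1 already uses all available history for other baseline variables. Item 1 drops patients with an earlier recorded dose, as section 6.2 intends; item 2 drops nobody from the main results. The sample-size figures do not change.

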6.2.2 Exclusion Criteria

No exclusion criteria will be applied.

6.3 Variables

NMOSD¹, NMOSD-associated conditions, comorbidities, and safety outcomes will be defined using the International Classification of Diseases (ICD), 9th or 10th revision codes or local modifications thereof. Medications will be defined using the Anatomic Therapeutic Chemical (ATC) codes or operation and procedure classification system (OPS) codes recorded in each data source (9,10).

6.3.1 New Inebilizumab Users

This is an observational study of real-world clinical practices and this protocol does not recommend the use of any specific treatments.

New inebilizumab users will be defined as patients with a first inebilizumab treatment (identified through first administration/prescription/dispensation, depending on how the information on the drug is collected in the data sources) during the study period with no previous inebilizumab treatment in 6 months prior to the index date.

Inebilizumab treatment (first and each subsequent administration/ prescription/ dispensation) will be identified by the ATC code (L04AA47 / L04AG10 from 2024). Information accompanying every drug administration/prescription/dispensation, including date and time, dose, indication, setting of healthcare and specialty of prescriber will be retrieved, if available.

6.3.2 Characterization Variables

Characteristics of new inebilizumab users at index date will include demographics, comorbidities, NMOSD-related clinical characteristics (disease duration, NMOSD core

¹The use of Orphanet coding system for rare diseases (<https://www.orpha.net/>) will be explored in the SAP as appropriate

syndromes, differential diagnoses, NMOSD-associated conditions, history of relapses), previous immunosuppressive therapies, and inebilizumab initiation characteristics (setting of healthcare and specialty of prescribers and treatment indication). Please note that the list of characterization variables may be refined based on the databases availability and specificity. Detailed operational definitions and lists of local codes will be provided in the SAP.

Demographic characteristics include sex, age at the index date and race/ethnicity, depending on availability.

Comorbidities will be assessed by the presence of an ICD-9/ICD-10 codes during the baseline period in the data sources (Table 6 in Annex 3). The codes for the following specific conditions are provided (Table 6 in Annex 3):

- Coronary heart disease
- Heart failure
- Cerebrovascular disease
- Lung disease
- Renal disease
- Rheumatic disease
- Diabetes
- Hypertension
- Malignancy
- Osteoporosis
- Anxiety
- Depression
- Skin ulcers/cellulitis
- Renal transplantation
- Infections

Charlson comorbidity index (CCI) (11) will be retrieved as an overall measure of the burden of concomitant diseases. A CCI code list will be provided in the SAP.

Prescriber of inebilizumab will be described in terms of the type of facility he/she works at (hospital or other) and specialty (e.g., Neurology, Neuroradiology, Ophthalmology, Rheumatology, Psychiatry, or other), if available.

NMOSD has a wide range of clinical and imaging manifestations, which overlap with those of MS and myelin-oligodendrocyte glycoprotein (MOG) antibody-associated disease. In a retrospective study of patients with NMOSD, 42.5% with available data were initially misdiagnosed with MS (12). NMOSD patients can be hidden within the large MS population, although after AQP4-IgG testing has become available, it is now easier to differentiate NMOSD from MS. In this study, all patients diagnosed with NMOSD at baseline or index date, regardless of other preceding or subsequent documented diagnoses, will be included if they initiate inebilizumab. The drug is expected to be prescribed only for those with NMOSD as the indication. However, the study population will be screened for differential diagnoses (Table 2). Treatment indication, if not directly available in the data sources, will be defined according to an algorithm that will distinguish between diagnoses such as NMO and/or other NMO core manifestations and differential diagnoses within a specified time-window around the index date. The algorithms will be described in detail in SAP.

Other NMOSD-related symptoms such as paroxysmal symptoms, loss of sensation, nausea/vomiting, bladder/bowel dysfunction will be described if available in the data sources.

Table 2 Diagnoses accepted to define NMOSD and differential diagnoses

Condition Description	Diagnosis ICD-9-CM Codes*	Diagnosis ICD-10-CM Codes*
Diagnosis codes recorded for NMO and/or other NMO core manifestations		
Neuromyelitis Optica	341.0	G36.0
Optic neuritis	377.3, 377.39	H46.1x, H46.8, H46.9
Retrobulbar neuritis	377.32,	H46.1, H46.10, H46.11, H46.12, H46.13
Acute (transverse) myelitis	341.2, 341.21, 341.22	G37.3
Differential Diagnoses		
Neuro-Behçet's disease	136.1	M35.2
Multiple sclerosis	340	G35
Parainfectious disorders	045.x, 047.9, 062, 063, 064, 066.41, 071, 138, 323.0, 323.1, 323.2, 323.4, 323.6, 357.0	A80.x, A81.x, A82.x, A83.x, A84.x, A85.x, A86.x, A87.x, A88.x, A89.x, B00.4, B02.0, B05.0, B10.0, B25.8, B26.2, B91, B94.1, G04.01, G14, G61.0

Abbreviations: ICD-9/ICD-10, 9th/10th Revision of International Classification of Diseases; NMO, neuromyelitis optica; NMOSD, neuromyelitis optica spectrum disorder; CM, Clinical Modification

*ICD-X-CM codes will be translated into local ICD-X codes and provided in SAP

NMOSD disease burden and clinical characteristics up to the index date will include the presence of each of the diagnoses part of the NMOSD core symptom, disease duration, AQP4 and MOG seropositivity, NMOSD-associated conditions, history of relapses, and previous acute and maintenance therapies.

Disease duration will be estimated as the difference between the index date and the first NMOSD diagnosis date.

Where available, laboratory results most recent to the index date will be used to classify patients according to the presence of autoantibodies against AQP4 and MOG. Patients will be classified as positive, negative or unknown serology. As it is recommended to repeat AQP4-antibody testing if the result is non-conclusive or negative, the presence of at least one positive result will be sufficient to classify the patient as positive. Thus, data on serology during follow-up will be also analysed to present the most updated serology status of the patients.

Information on spinal cord and brain Magnetic Resonance Imaging (MRI) scans performed in the previous year will be extracted whenever available in the data sources. Patients will be defined as having had performed spinal MRI only, brain MRI only, spinal and brain MRI or no MRI scan in the previous year.

NMOSD as an autoimmune disease has been reported to coincide with other disorders including systemic autoimmune diseases, organ-specific autoimmune diseases, and other diseases with possible immunologic pathogenesis (13). The association of clinical or even subclinical autoimmunity is a supportive feature for the diagnosis of the disease (14).

NMOSD-associated conditions listed below will be identified by the respective ICD-9/ICD-10 codes (**Error! Reference source not found.** in Annex 3):

- Hypothyroidism
- Pernicious anemia
- Ulcerative colitis
- Myasthenia gravis
- Idiopathic thrombocytopenic purpura
- Hemiplegia/paraplegia
- Bladder dysfunction
- Neuropathic pain
- Antiphospholipid syndrome
- Sarcoidosis
- Scleroderma
- Sjogren’s syndrome
- Systemic lupus erythematosus
- Dorsalgia
- Disorders of lipoprotein metabolism and other lipidemias
- Other acute disseminated demyelination
- Disorders of refraction and accommodation
- Visual disturbances
- Disturbances of skin sensation
- Somatoform disorders
- Other dorsopathies, not elsewhere classified

History of relapses will be ascertained depending on available data in the data sources (e.g., using documented relapse episodes as defined by individual disease-specific registries or considering the previous use of acute treatments such as intravenous corticosteroids, intravenous immunoglobulin or plasmapheresis therapy, or hospital admission with selected principal diagnoses) and will be defined in detail in SAP. Patients will be characterized according to the number of relapses in the previous 1 and 2 years (none, one, two or more).

Baseline use of **acute treatments** will include intravenous corticosteroids, intravenous immunoglobulin or plasmapheresis therapy in a 6-month period prior to the index date ([Table 7](#) NMOSD-Associated Conditions)

NMOSD-associated Conditions	Diagnosis ICD-9-CM Codes*	Diagnosis ICD-10-CM Codes*
Hypothyroidism	244.x	E89.0, E03.2, E03.8, E03.9
Pernicious anemia	281.0, 281.1	D51.x
Ulcerative colitis	556.x [excl. 556.2 and 556.3]	K51.xx [excl. K51.2x and K51.3x]
Myasthenia gravis	358.0x	G70.0x
Idiopathic thrombocytopenic purpura	446.6	M31.1
Hemiplegia/paraplegia	334.1, 342.x, 343.x, 344.0x-344.6x, 344.9	G11.4, G81.xx, G80.x, G83.0, G83.1x, G83.2x, G83.3x, G83.4, G83.9, G82.xx

NMOSD-associated Conditions	Diagnosis ICD-9-CM Codes*	Diagnosis ICD-10-CM Codes*
Bladder dysfunction	788.30, 788.31, 788.33, 788.34, 788.36, 788.37, 788.39-788.43, 596.xx	N30.xx, N31.x, N32.xx, N33
Neuropathic pain	353.x, 354.x, 355.x, 356.x, 357.x, 250.6, 729.2, 782	E08.40-E08.42, E09.40, E09.42, E10.40-E10.42, E11.40-E11.42, E13.40-E13.42, G50.0, G50.1, G54.x, G55.x, G56.x, G57.x, G58.x, G60.x, G61.x, G62.x, G63, G64, G65.x, G90.5x, M05.5x, M79.2, M54.1, R20
Antiphospholipid syndrome	289.81	D68.61
Sarcoidosis	135	D86.xx
Scleroderma	357.4, 359.6, 517.2, 701.0, 710.1	M34.xx, L90.0, L94.0, L94.1, L94.3
Sjogren's syndrome	710.2	M35.0x
Systemic lupus erythematosus	710	M32.xx
Dorsalgia	724.5	M54
Disorders of lipoprotein metabolism and other lipidemias	272.0, 272.1, 272.2, 272.3, 272.4, 272.5, 272.9	E78
Other acute disseminated demyelination	341.9	G36.9
Disorders of refraction and accommodation	367	H52
Visual disturbances	368	H53
Disturbances of skin sensation	782	R20
Somatoform disorders	300.81	F45
Other dorsopathies, not elsewhere classified	723.2, 723.3, 723.8, 723.9	M53

Abbreviations: ICD-9/ICD-10, 9th/10th Revision of International Classification of Diseases; CM, Clinical Modification; NMOSD, Neuromyelitis optica spectrum disorder

*ICD-X-CM codes will be translated into local ICD-X codes and provided in SAP

Table 8 in Annex 3). To characterize **maintenance therapy** in the same period, the use of recommended drugs such as oral corticosteroids, immunosuppressants, B-Cell targeting therapies, tocilizumab, eculizumab, satralizumab (Table 9 in Annex 3) and other immunosuppressive treatments (Table 10 in Annex 3) will be retrieved.

The use of pain medications in the 6 months prior to the index date will be determined taking into account drugs specified in Table 11 in Annex 3.

